7.1.3 Descriptive Summaries of Continuous Variables

Descriptive summaries of continuous variables in terms of baseline values, change or percent change from baseline values will be provided by treatment group and overall, as applicable. These summaries may include the estimations of means, medians, standard deviations and ranges, as applicable.

7.1.4 Descriptive Summaries of Categorical Variables

Descriptive summaries of categorical variables will consist of frequencies and percentages for each treatment group and overall, as applicable.

7.1.5 Mixed effects Model with Repeated Measures

7.1.5.1 Model Specification

A mixed effect model with repeated measures analysis using ‘direct likelihood’ will be performed. The SAS procedure PROC MIXED will be used.

The dependent variable will be the change from baseline to each Visit t included in the model for efficacy endpoints examining changes from baseline. For analyses of parameters in terms of percent change from baseline at Visit t, values will first be transformed to logarithms and the results will be expressed as geometric mean percent changes from baseline. The dependent variable will be the natural logarithms (Ln) of the post-baseline to baseline ratios. The model estimates will be back transformed to original values using the formulae detailed in [Table 7.1.2-1](#).

The preferred model will include the fixed categorical effects of treatment, visit, randomization stratification factors (i.e. one term for each combination of the stratification factors of hydroxychloroquine and oral corticosteroid use based on IVRS) and treatment-by-visit interaction, as well as the continuous fixed covariates of baseline measurement and baseline measurement-by-visit interaction. For parameters analyzed as percent change from baseline, the natural logarithm of the baseline values will be used in the above model specification. An unstructured matrix for the within-subject error variance-covariance will be used. The denominator degrees of freedom will be calculated according to the Kenward-Roger method.

In case of non-convergence of the preferred model or memory space issues the following back-up models are defined:

- 1) The first backup model is the same as the preferred model but the Kenward-Roger method will be replaced by Satterthwaite approximation.
- 2) The second backup model is the same as the preferred model but without the term for baseline measurement-by-visit interaction.

The second back-up model will only be provided if the first back-up model does not converge or has memory issues.

The model will provide least-squares mean estimates, standard errors and 2-sided 95% confidence intervals for mean change at all time points within and between treatments. Where applicable, for specific visits, the t-statistic corresponding to the Type III sums of squares for the differences in the least squares means will be used to obtain p-values for treatment group comparisons.

7.1.5.2 Model Assumption Assessment

The assumptions underlying the longitudinal repeated measures analysis model will be checked, if specified in Section 7.5. This section also details the steps to follow in case these assumptions would not be satisfied.

Assessment of Treatment-by-Baseline Interaction:

Treatment-by-baseline interaction will be assessed for the Visit 85 estimates. In the model defined in 7.1.5.1, the interaction will be tested by including the treatment-by-baseline interaction.

The following contrast statements will be used of testing for interaction.

- Contrast coefficients for all visits but Visit 85 will be zero.
- Contrast coefficients at Visit 85 are presented in Table 7.1.5.2-2.

Table 7.1.5.2-2: Contrast Coefficients for the treatment-by-baseline interaction for visit 85 estimates

Treatment by baseline interaction	Contrast Coefficients
Lulizumab by baseline value	1
BMS-986142 by baseline value	0
Placebo by baseline value	-1
Lulizumab by baseline value	0
BMS-986142 by baseline value	1
Placebo by baseline value	-1

The test for interaction will be performed at the 0.10 level of significance. If significant, the interaction will be assessed as qualitative or quantitative. Assessment of the interaction type will be based on regression lines plotted for each treatment group. The intercepts and slopes for these regression plots will be obtained from the analysis model including the interaction term. The intercepts will be estimated by the least squares means. The abscissa of the plots will range from the minimum baseline value from all subjects included in the analysis to the maximum baseline value.

If the regression lines do not cross, or the crossing is judged not severe (i.e., the crossing occurs near the boundary or beyond the range of baseline values), then the interaction will be considered quantitative and this does not compromise the validity of the treatment comparisons. In this case, the treatment comparisons will be made using the model without the interaction term.

Otherwise, the interaction will be considered qualitative and treatment comparisons will not be presented as a result of the complete model. In this case, the impact of the baseline value on treatment effect will be investigated by summarizing the data in subsets defined by baseline categories.

Assessment of Treatment-by-Randomization Stratification Factor Interaction:

Treatment-by-combination of stratification factors interaction for estimates at Visit 85 will be assessed using method described below. In the model defined in 7.1.5.1, the interactions will be tested by including the treatment-by-combination of stratification factor interaction and appropriate contrast statement for testing the interaction in the visit 85 estimates. Contrast coefficients for all visits but Visit 85 will be zero. The tests for interaction will be performed at the 0.10 level of significance.

Outlier Detection:

Specifically, an outlier is defined as an observation with a residual that is more than three times the interquartile range above the 75th percentile or below the 25th percentile. Outliers will be identified based on diagnostics performed for the primary efficacy outcome measure using standardized residuals from the mixed effect model with repeated measurement. These diagnostics will be based on the box plot. If outliers are present, then additional sensitivity analyses will be performed with the outliers excluded, in order to assess their impact on the results.

Adjustments for baseline imbalances:

Adjustments for baseline imbalances between treatment groups in the longitudinal repeated measures model may be performed as a sensitivity analysis: baseline characteristics for which a clinically important imbalance exists between the treatments will be identified. If such imbalances exist, an adjustment will be performed by including the corresponding baseline characteristics as additional covariates in the longitudinal repeated measures model. This will allow the assessment of the importance of these imbalances on the treatment group comparisons.

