8.4.2 Efficacy Analyses

8.4.2.1 Primary Efficacy Analyses

The mixed effects model with repeated measures (MMRM) will be used to model the change from baseline in ESSDAI score over time for all treatment arms. Details of the model will be given in the statistical analysis plan. The least square means of the differences of Week 12 change in ESSDAI from baseline between each active treatment and the placebo will be estimated and their corresponding two-sided 95% confidence intervals will be provided. In addition, as part of the secondary objective, similar outputs will be provided for the changes in ESSDAI score at Weeks 4 and 8.

The Hochberg's step-up procedure will be used to adjust the multiplicity due to the comparison of two active treatments (lulizumab or BMS-986142) to the placebo arm in the primary endpoint (ie, change from baseline in ESSDAI at Week 12). The corresponding adjusted p-values for the Hochberg procedure will be provided.

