7.5.1 Primary efficacy analysis

The EULAR Sjögren's Syndrome Disease Activity Index (ESSDAI) is a systemic disease activity index that was designed to measure disease activity in subjects with pSS (see Protocol Appendix 3).³³ The ESSDAI parameters are assessed by the investigators and the results from each assessment are recorded in site source records as well as entered into the corresponding eCRF. The ESSDAI total score will be calculated as described in [section 8.6](#)

The primary efficacy endpoint is change from baseline ESSDAI score at Week 12.

The mixed effects model with repeated measures (MMRM) will be used to model the change from baseline in ESSDAI score over time for all treatment arms. Details of the model are presented in [section 7.1.5.1](#).

The least square means of the differences of Week 12 change in ESSDAI from baseline between each active treatment and the placebo will be estimated and their corresponding two-sided 95% confidence intervals will be provided.

The Hochberg's step-up procedure will be used to adjust the multiplicity due to the comparison of two active treatments (lulizumab or BMS-986142) to the placebo arm. The corresponding adjusted p-values for the Hochberg procedure will be provided.

The model assumption assessment will be performed following the methodology described in [section 7.1.5.2](#).

In addition, the same model will be used to provide estimates for the changes in ESSDAI score at each time point of assessment as per protocol.

In case that more than 10% of subjects in any treatment group have a relevant protocol deviation, leading to exclusion of efficacy data, then this analysis will be repeated excluding efficacy data from subjects with relevant protocol deviations, as described in [APPENDIX 1](#).

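### SAP 7.1.5.2 can withhold the primary treatment comparison after a 0.10-level interaction test, while Protocol 8.4.2.1 and SAP 7.5.1 promise it without condition

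*SAP*

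**What the plan says.** SAP 7.1.5.2 applies only where SAP 7.5 calls for it, and SAP 7.5.1 does so for the primary endpoint: "The model assumption assessment will be performed following the methodology described in" that section.

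On the treatment-by-baseline interaction at Visit 85, SAP 7.1.5.2 states: "The test for interaction will be performed at the 0.10 level of significance". A significant result is then classified by eye from regression lines plotted for each arm.

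- **Quantitative:** the lines do not cross, or "the crossing is judged not severe (i.e., the crossing occurs near the boundary or beyond the range of baseline values". Comparisons then come from the model without the interaction term.
- **Qualitative:** in every other case, "the interaction will be considered qualitative and treatment comparisons will not be presented as a result of the complete model". The influence of baseline "will be investigated by summarizing the data in subsets defined by baseline categories".

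Three other places describe the same output with no condition attached:

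- Protocol 8.4.2.1 says the Week 12 differences "between each active treatment and the placebo will be estimated and their corresponding two-sided 95% confidence intervals will be provided".
- SAP 7.5.1 repeats this and adds: "The corresponding adjusted p-values for the Hochberg procedure will be provided".
- SAP 7.1.5.1 says: "The model will provide least-squares mean estimates, standard errors and 2-sided 95% confidence intervals for mean change at all time points", both within and between treatments.

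**The concern.** In the qualitative branch one instruction says to report the primary comparison and another says not to. The trial's only multiplicity-controlled result would then depend on which sentence is followed, and that choice would be made after the lines by arm have been seen.

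The trigger is also loosely defined. The SAP does not say:

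- what *complete model* means;
- how close to the edge of the baseline range a crossing must be to be excused;
- which pairs of lines count (each active arm against placebo, or also the two active arms against each other);
- which baseline categories would be used (SAP Table 7.3.2-2 lists the ESSDAI total as continuous only);
- who judges the crossing, and whether that person is blinded.

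The other checks in SAP 7.1.5.2 are milder. Outliers and baseline imbalance lead only to sensitivity analyses, and the stratification-factor interaction test has no stated consequence. Only the treatment-by-baseline check replaces the primary comparison.

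**Working it through.** **1. The passages side by side, when the test is significant and the crossing is not mild**

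| Source | Instruction for the Week 12 comparison |
|---|---|
| Protocol 8.4.2.1 | Provide differences, 95% CIs and Hochberg-adjusted p-values |
| SAP 7.5.1 | Provide the same |
| SAP 7.1.5.1 | The model provides between-treatment estimates and CIs |
| SAP 7.1.5.2 | Do not present treatment comparisons; summarise by baseline subset |

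**2. The plan's own figures (Protocol 8.1)**

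Two-sided t-test at 0.05, difference 3, noncentrality = 3 / (SD × √(2/n)).

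- n = 25, SD 3.2: 3 / (3.2 × 0.2828) = 3.31 on 48 df; power 90.1% (stated: approximately 90%).
- n = 40, SD 4.8: 3 / (4.8 × 0.2236) = 2.80 on 78 df; power 78.8% (stated: 79%).

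Both reproduce. They assume that the comparison is always reported.

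**3. How often the rule fires with no true interaction**

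One joint 2-df test at 0.10 is significant in 10% of trials by construction. Withholding also needs a severe crossing. For arms g and h with fitted intercepts a and slopes b, the lines cross at

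x = −(a_g − a_h) / (b_g − b_h).

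If the two arms have the same mean response, this point falls near the baseline mean, so almost every significant test qualifies. A 3-point effect pushes the active-placebo crossing outwards. For example, with baseline SD 3 and n = 25, the standard error of a slope difference is about 3.2 × √(2/(24 × 9)) = 0.31. A single contrast just significant at 0.10 has a slope difference of about 1.67 × 0.31 = 0.51, and its crossing lies about 3 / 0.51 = 5.8 points from the mean.

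**4. Simulation**

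There were 20,000 trials per setting, using a Week 12 ANCOVA in place of the Visit 85 MMRM contrast. From the Protocol: 25 per arm, SD 3.2 (used as residual SD) and a 3-point effect. Assumed, because the documents give no baseline distribution: baseline = 5 + gamma, rounded, with mean/SD 8/2.5, 9/3 or 10/4.5, and equal true slopes.

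Share of trials withheld, with a severe crossing taken as one inside the central 80% of the width of the baseline range:

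| Truth | Active-placebo pairs | Any pair |
|---|---|---|
| Neither drug works | 9.5-9.9% | 9.7-10.2% |
| One works by 3 points | 8.5-9.2% | 8.7-9.4% |
| Both work by 3 points | 5.2-5.8% | 8.7-9.2% |

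Letting severe range from the central 40% to the central 90% of the width gives 4.2-10.3%, 4.6-9.8% and 4.0-9.5% for the three rows. At 40 per arm and SD 4.8 the withheld share is 3-10%.

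A second simulation (6,000 trials per setting; baseline gamma with mean about 10, or uniform 5 to 15; active-placebo pairs) defined severe as lying between the 10th and 90th baseline percentiles. At 25 per arm it gave about 10% (neither works), 8.7-9.2% (one works) and 3.3-4.0% (both work). Counting any crossing within the observed range, the last figure is 6.2-7.0%.

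**5. What is lost**

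Over the central 40-90% rules, the chance of a reported Hochberg-significant result falls by 4-8 points from about 85% if one drug works, and by 4-9 points from about 94% if both work. Withheld trials are about as likely to be significant as the rest: 82.0-86.3% against 84.6-85.2% (one works), and 89.3-95.2% against 93.8-94.2% (both work). If neither works, the false-positive rate is 4.7-5.0%, and it falls by 0.2-0.5 points when withheld trials are not counted.

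Testing the two contrasts in SAP Table 7.1.5.2-2 separately at 0.10 would raise withholding to about 17-18% if neither drug works. The SAP does not say that this is intended.

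**The case against.** **The wording may be narrower than it looks.** *Complete model* could mean the model with the interaction term, so that only that model's comparisons are dropped and the SAP 7.5.1 outputs stand. The phrase is ambiguous and this reading is possible. But SAP 7.1.5.2 assigns the model without the interaction to the quantitative case only. For the qualitative case it names no comparison, and no other section restores one.

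**It may be a pre-specified exception.** Protocol 8.4.2.1 leaves details of the model to the SAP, and SAP 7.5.1 itself brings in the checks. Within the SAP, a specific rule can qualify a general one. The Protocol, however, delegates the model's details, not whether its primary result is reported.

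**Other results would survive.** The Week 12 responder comparisons in SAP 7.5.2.1 are not subject to the check, so the trial would not be left without efficacy results. But SAP 7.5.2.2 refers Week 12 ESSDAI back to SAP 7.5.1, and the responder p-values are nominal.

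**An average effect can mislead under a true qualitative interaction.** This is a reason to show effects by baseline beside the primary result. It is not a reason to withhold that result after a 0.10-level test with 25 per arm.

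**The rates rest on assumptions.** This stands. Varying the common slope with the residual SD fixed tests nothing, because slope differences and crossing points do not change. The Protocol's 3.2 reads more naturally as the SD of change. Holding it so, with slope −0.6, baseline 10/4.5, both drugs working and active-placebo pairs only, lowers withholding from about 5.3% to 3.4% (central 80%) and from about 4.2% to 1.7% (central 40%). A narrow percentile-based definition would lower that setting further. The rates if neither drug works do not change.

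**Conclusion.** The concern holds and should be resolved before unblinding. The conflict between SAP 7.1.5.2 and the unconditional commitments in Protocol 8.4.2.1 and SAP 7.5.1 is in the text and depends on no simulation.

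Its size does depend on assumptions. With one joint test and no true interaction, the primary comparison would be withheld in about 9-10% of trials when neither drug or only one works, under a central-80% rule. When both work it is about 3-9%, depending on which pairs count and how severe is defined. Narrower rules lower these figures, to about 2% or less in the most favourable setting. They rest on an assumed baseline distribution and a single-visit approximation to the MMRM.

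The harm is loss of a valid primary result through chance and an unspecified judgement. There is no inflation of type I error, no clear tendency to remove null results, and no error in the stated power calculation.

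**What to change.** In SAP 7.1.5.2, delete the rule that comparisons are not presented. State instead that the Week 12 differences, 95% confidence intervals and Hochberg-adjusted p-values from the SAP 7.1.5.1 MMRM are always reported as the primary result, whatever the interaction assessment shows.

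Keep the treatment-by-baseline assessment as supportive and present it alongside: treatment effects at chosen baseline ESSDAI values, or in baseline categories named in the SAP before unblinding. State whether the assessment is one joint test or two separate tests. The same supportive-only wording could cover the treatment-by-stratification-factor test, which at present has no stated consequence.

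The core change is about two sentences in the SAP. It needs no extra data or patients and no change to the Protocol, which already promises the result.

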7.1.6 Kaplan-Meier Curve and Estimates for Time-to-Event Analyses

Kaplan-Meier plots³¹ of time to event variables will be displayed by treatment group. Unless otherwise specified, the plot will be presented only when there are at least 5 events in one treatment group. Additionally, a table will accompany the plot and will display the Kaplan-Meier estimates of the cumulative proportion (with 95% CI calculated based on Greenwood's method³² when applicable) of subjects with event at specific time points by treatment group. If the estimated lower bound of 95% CI is below 0 or the estimated upper bound of 95% CI is over 1, then it will be restricted to 0 or 1 respectively.

7.1.7 Test for Proportion of Subjects with a Characteristic at Visit *t*

In cases that a comparisons between proportions is needed, the Chi-square test will be used to compare the proportions between each of the active treatment arms and the placebo arm. The

Chi-square p-value will be provided for each comparison between the active treatment and the placebo arm. In addition, the difference of in proportions between each active treatment and the placebo arm will be estimated and their corresponding 95% confidence interval will be calculated.

The construction of confidence intervals for binary variables will be based on normal approximation if the number of the events in each individual treatment arm is at least 5. Otherwise, confidence interval using an exact method will be provided. The exact confidence intervals for binary variable within treatment group and between treatment groups will be constructed.

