8 STATISTICAL CONSIDERATIONS

8.1 Sample Size Determination

The sample size calculation is based on the power to compare change from baseline in ESSDAI at Week 12 between active treatment arms (lulizumab or BMS-986142) and the placebo arm. With a two-sided two-sample t-test at significance level 0.05, data from 25 treated subjects per arm will provide approximately 90% power to detect a placebo-adjusted 3-point decrease from

baseline for each active treatment group, assuming common standard deviations of 3.2.⁶⁶ In addition, the Hochberg's step-up procedure will be used to adjust the multiplicity due to the comparison of two active treatment arms (lulizumab or BMS-986142) to the placebo arm.

The primary efficacy analysis will be conducted on all randomized subjects who received at least one dose of study drug.

An interim analysis will be conducted after at least 30 subjects reach Week 12 (complete 12 weeks of treatment) and complete the specified assessments for ESSDAI. The interim analysis will be conducted in a fully blinded manner such that treatment group assignments of study subjects are not known and are not used in any manner in the analysis. A blinded examination of the variance of the primary endpoint will be performed and compared to the assumption used in planning the study. If this comparison suggests the initial assumption was substantially too low, the total study sample size may be increased by up to 45 additional subjects (ie, to a maximum of 120 subjects in total) to maintain adequate study power.^{67,68,69} Regardless of the outcome from the blinded examination of variability, the study sample size will not be decreased. A maximum study sample size of 120 subjects in total, ie, 40 subjects per arm, can provide each active treatment arm 79% power to detect a placebo-adjusted 3-point decrease from baseline for common standard deviations as large as 4.8, using a two-sided two-sample t-test comparing each active treatment arm to placebo at significant level 0.05.

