7.5.2.1 Categorical Endpoints

For each of the following categorical secondary endpoints, the estimate and its corresponding two-sided 95% confidence interval will be calculated for the proportion for each treatment arm. In addition, differences of the proportions between each active treatment arm and the placebo arm will be evaluated and their corresponding two-sided 95% confidence intervals and nominal p-values will be provided.

- Proportion of subjects with a ≥ 3 point improvement from baseline in ESSDAI at Week 12
- Proportion of subjects with a ≥ 1 point improvement from baseline in ESSPRI at Week 12
- Proportion of subjects with both ≥ 3 point improvement from baseline in ESSDAI and ≥ 1 point improvement from baseline in ESSPRI at Week 12

The subjects that have discontinued the study prematurely or have missing assessments for ESSDAI or ESSPRI at Week 12, they will be counted in these analyses as having no improvement since baseline.

The same analysis will be repeated at each timepoint of assessment of ESSDAI and ESSPRI as per protocol. For these analyses no nominal p-values will be produced.

For the calculation of ESSDAI refer to [section 8.6](#). For the calculation of ESSPRI refer to [section 0](#).

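### The interval rule for responder proportions tests only the event count, so a per-arm interval can pass 100% or have zero width if an arm responds at roughly 75% or more (minor)

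*SAP*

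**What the plan says.** SAP 7.1.7 chooses the interval method by the event count alone. Intervals are "based on normal approximation if the number of the events in each individual treatment arm is at least 5". When the count falls short of that threshold, the section turns to its fallback: "Otherwise, confidence interval using an exact method will be provided". The section does not name the normal-approximation method and does not restrict limits to the range 0 to 1. SAP 7.1.6, just before it, does restrict its limits, but only for Kaplan-Meier estimates.

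SAP 7.5.2.1 applies this to three Week 12 responder endpoints: ESSDAI improvement of at least 3 points, ESSPRI improvement of at least 1 point, and both together. For each, "the estimate and its corresponding two-sided 95% confidence interval will be calculated for the proportion for each treatment arm", and between-arm differences also get intervals. The analysis is repeated at the other ESSDAI and ESSPRI assessments. For subjects who discontinue or lack a Week 12 assessment, "they will be counted in these analyses as having no improvement since baseline".

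Protocol 8.1 plans 25 treated subjects per arm, with a ceiling after sample size re-estimation: "A maximum study sample size of 120 subjects in total, ie, 40 subjects per arm". Neither document gives an expected responder rate.

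**The concern.** The normal approximation to a binomial proportion is equally poor with few events and with few non-events. A rule that guards one side only treats mirror-image data differently. An arm with 2 responders in 25 gets an exact interval; an arm with 2 non-responders in 25 gets a normal-approximation interval.

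At stake is the stated precision of a responder proportion in an arm that does well. There the reported limits could be impossible or of zero width, or the interval could cover the true rate less often than 95%.

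**Working it through.** **Inputs.** n = 25 per arm (Protocol 8.1), or 40 at the maximum; two-sided 95% level (SAP 7.5.2.1); switch at 5 events (SAP 7.1.7). Two assumptions: normal approximation means the Wald interval, and the condition is judged on the arm whose interval is being built. True responder rates are assumed and shown as a range.

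**The plan's own figure first.** Protocol 8.1 states that "25 treated subjects per arm will provide approximately 90% power" for a 3-point difference with SD 3.2. The noncentrality is 3 / (3.2 × √(2/25)) = 3.31 on 48 df, giving 90.1% power at two-sided 0.05. With 40 per arm and SD 4.8 it is 3 / (4.8 × √(2/40)) = 2.80 on 78 df, giving 78.8% against the stated 79%. Both reproduce, so the arm sizes used here are the plan's.

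**Limits.** Wald: p ± 1.96 × √(p(1−p)/n). For 22/25, p = 0.88, the standard error is √(0.88 × 0.12 / 25) = 0.0650, and the limits are 0.88 ± 0.127.

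| Responders | SAP rule (Wald) | Exact (Clopper-Pearson) |
|---|---|---|
| 22/25 | 75.3% to 100.7% | 68.8% to 97.5% |
| 23/25 | 81.4% to 102.6% | 74.0% to 99.0% |
| 24/25 | 88.3% to 103.7% | 79.6% to 99.9% |
| 25/25 | 100% to 100% | 86.3% to 100% |

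The upper limit passes 1 when (1−p) < 1.96 × √(p(1−p)/n), that is, when the number of non-events is above zero and below 3.84 × p. At high rates this means 1 to 3 non-events, whatever n is. At 40 per arm, 37/40 to 39/40 therefore exceed 100%, and 40/40 has zero width.

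**Coverage.** For true rate π, coverage is the sum over x = 0 to n of the binomial probability of x, counting only those x whose interval contains π. The interval is Wald if x ≥ 5 and Clopper-Pearson otherwise.

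| True rate | n = 25, SAP rule | n = 25, non-event condition added | n = 25, Wilson | n = 40, SAP rule |
|---|---|---|---|---|
| 75% | 0.893 | 0.982 | 0.938 | 0.945 |
| 80% | 0.884 | 0.979 | 0.926 | 0.905 |
| 85% | 0.899 | 0.975 | 0.957 | 0.939 |
| 90% | 0.919 | 0.991 | 0.967 | 0.915 |
| 95% | 0.721 | 0.999 | 0.966 | 0.868 |

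At the mirror rates of 25%, 20% and 15% with n = 25, the SAP rule covers 0.982, 0.979 and 0.975, because few events trigger the exact method.

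Coverage oscillates with the true rate, so averages are fairer than single points. Under the SAP rule the mean over 75% to 85% is about 0.92 at n = 25 and 0.925 at n = 40. Over 70% to 95% it is about 0.90 and 0.917.

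At 50%, 55%, 60%, 65% and 70% with n = 25, coverage is 0.957, 0.930, 0.936, 0.942 and 0.949. The same sum on a finer grid over that range averages 0.93, with dips to 0.90; this is ordinary Wald behaviour at this sample size, and few non-events are not its main cause.

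**How often the gap is reached, n = 25.** The chance of fewer than 5 non-events is 0.05% at a true rate of 50%, 0.9% at 60%, 9% at 70%, 21% at 75% and 42% at 80%. The chance of an upper limit above 100% is 3% at 70%, 23% at 80% and 69% at 90%. The chance of a zero-width interval is 0.01% at 70%, 0.4% at 80% and 7.2% at 90%.

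**What rate might occur.** Assume a normally distributed ESSDAI change with SD 3.2, ignoring that the score takes whole numbers. The share improving by at least 3 points is Φ((m − 3)/3.2) for mean improvement m: 50% at m = 3, 62% at 4, 73% at 5 and 83% at 6. A rate of 75% needs m = 3 + 0.674 × 3.2 = 5.2 points. Since the planned 3 points are placebo-adjusted, placebo would have to improve by about 2.2 points. No comparable input exists for ESSPRI.

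**Differences between arms.** Wald difference intervals at n = 25 cover 0.911 to 0.980 over eight pairs of rates between 40% and 95%. The lowest value is at 95% v 90%. No limit exceeds 100%, but the width is zero if both arms are at 100%.

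**The case against.** The strongest counter-argument is that the harm needs response rates the documents never predict. The planning effect does not by itself imply 75% responders, counting missing as not improved lowers every rate, and the combined endpoint cannot exceed the lower of its two components. This stands, and it limits the point to a conditional one.

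A reader might infer that the responder intervals generally cover about 88%. The documents do not support that. The value 0.884 belongs to a true rate of exactly 80% at 25 per arm, and that rate is an assumption made here. Wilson itself covers only 0.926 at that rate.

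The text also allows other readings:
- Normal approximation need not mean Wald. Wald is the usual reading; if a score interval was meant, the SAP should name it.
- The condition on each individual arm could mean that every arm needs 5 events. A sparse placebo arm would then trigger exact intervals throughout, with probability 42% at a 20% placebo rate and 21% at 25%. That would sometimes mask the gap, for a reason unrelated to it.
- The last sentence of 7.1.7 mentions exact intervals without a condition. Read as always applying, it would make the switch pointless; in context it describes the fallback.
- Limits above 100% would probably be truncated in reporting. Truncation cures neither the lost coverage nor the zero-width interval.

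**Conclusion.** The rule is a stated one and it is asymmetric. At 25 per arm, read as Wald, it gives impossible per-arm limits at 22 to 24 responders and a zero-width interval at 25. Coverage falls to about 0.88 to 0.90 at the assumed rates of 75%, 80% and 85%. Going to 40 per arm reduces the loss but does not remove it.

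The point is minor. It matters only if an arm responds at roughly 75% or more. It concerns mainly single-arm intervals for three secondary endpoints, which carry no multiplicity adjustment. Protocol 8.4.2.2 calls the between-arm differences exploratory.

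A reader might also infer that the treatment comparison or the trial's conclusion is compromised. That does not follow: difference intervals are little affected, the responder p-values come from a chi-square test, and the primary mixed-model analysis of ESSDAI change does not use this rule.

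**What to change.** In SAP 7.1.7, change the condition to at least 5 events and at least 5 non-events in each arm, otherwise exact, and name the normal-approximation method. Say whether a per-arm interval depends on that arm's counts alone. Alternatively, drop the switch and name Wilson intervals for each arm and Newcombe or Miettinen-Nurminen intervals for differences.

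Either is a one-sentence edit using standard software options, with no new data and no design change; it should be made before unblinding. The cost is somewhat wider intervals at high response rates. For 22/25 the width goes from 25.4 points (100.7 − 75.3) to 28.7 points (97.5 − 68.8) with the exact fallback. That fallback is conservative, with coverage of about 0.98 at a true rate of 80%. Wilson stays closer to 95% on average but can fall slightly below it, as at 80%.
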